6.3.3 Management of RAD001 toxicities

Known Undesirable Side Effects of RAD001

Adverse events most frequently observed with RAD001 are rash, stomatitis/oral mucositis, fatigue, headache, anorexia, nausea, vomiting, diarrhea, ocular toxicity and infections. Non-infectious pneumonitis has also been observed. Overall, the most frequently observed laboratory abnormalities include neutropenia, thrombocytopenia, hypercholesterolemia, and/or hypertriglyceridemia. The majority of these AEs have been of mild to moderate severity (CTC grade 1-2).

Table 6-2 Criteria for dose-modification in case of suspected RAD001 toxicity and re-initiation of RAD001 treatment

Toxicity	Actions
Non-hematological toxicity Grade 2 (except pneumonitis, refer to Table 6.3)	If the toxicity is tolerable to the patient, maintain the same dose. If the toxicity is intolerable to patient, interrupt RAD001 until recovery to grade \leq 1. Then reintroduce RAD001 at same dose. If event returns to grade 2, interrupt RAD001 until recovery to grade \leq 1. Then reintroduce RAD001 at the lower dose level.
Grade 3 (except hyperlipidemia)	Interrupt RAD001 until recovery to grade \leq 1. Then reintroduce RAD001 at the lower dose level. For pneumonitis, consider the use of a short course of corticosteroids (see table 6.3).
Grade 3 hyperlipidemia (hypercholesterolemia and/or hypertriglyceridemia)	Should be managed using standard medical therapies.
Grade 4	Discontinue RAD001.
Hematological toxicity Grade 2 Thrombocytopenia (platelets $<$ 75, \geq 50x10 ⁹ /L)	Interrupt RAD001 until recovery to grade \leq 1 (platelets \geq 75x10 ⁹ /L). Then reintroduce RAD001 at initial dose. If thrombocytopenia again returns to grade 2, interrupt RAD001 until recovery to grade \leq 1. Then reintroduce RAD001 at the lower dose level.
Grade 3 Thrombocytopenia (platelets $<$ 50, \geq 25x10 ⁹ /L)	Interrupt RAD001 until recovery to grade \leq 1 (platelets \geq 75x10 ⁹ /L). Then resume RAD001 at one dose level lower. If grade 3 thrombocytopenia recurs, discontinue RAD001.
Grade 4 Thrombocytopenia (platelets $<$ 25x10 ⁹ /L)	Discontinue RAD001.

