Grade 3 Neutropenia (neutrophils $< 1, \geq 0.5 \times 10^9/L$)	Interrupt RAD001 until recovery to grade ≤ 1 (neutrophils $\geq 1.5 \times 10^9/L$). Then resume RAD001 at the initial dose. If ANC again returns to Grade 3, hold RAD001 until the ANC $\geq 1.5 \times 10^9/L$. Then resume RAD001 dosing at the lower dose level. Discontinue patient from study therapy for a third episode of grade 3 neutropenia.
Grade 4 Neutropenia (neutrophils $< 0.5 \times 10^9/L$)	Interrupt RAD001 until recovery to grade ≤ 1 (neutrophils $\geq 1.5 \times 10^9/L$). Then resume RAD001 at the lower dose level. If grade 3 or grade 4 neutropenia occurs despite this dose reduction, discontinue RAD001.
Grade 3 febrile neutropenia (not life-threatening)	Interrupt RAD001 until resolution of fever and neutropenia to grade ≤ 1 . Hold further RAD001 until the ANC $\geq 1,500/mm^3$ and fever has resolved. Then resume RAD001 at the lower dose level. If febrile neutropenia recurs, discontinue RAD001.
Grade 4 febrile neutropenia (life-threatening)	Discontinue RAD001.
Any hematological or non-hematological toxicity requiring interruption for ≥ 3 weeks	Discontinue RAD001.

Monitoring of RAD001 suspected toxicities

Patients whose treatment is interrupted or permanently discontinued due to an adverse event or abnormal laboratory value suspected to be related to RAD001 must be followed at least weekly via telephone until the adverse event or abnormal laboratory value resolves or returns to grade 1. If a patient requires a dose delay of > 21 days from the intended day of the next scheduled dose, then the patient must be discontinued from the study.

Management of stomatitis/oral mucositis/mouth ulcers

Stomatitis/oral mucositis/mouth ulcers due to RAD001 should be treated using local supportive care. Please note that investigators in earlier trials have described the oral toxicities associated with RAD001 as mouth ulcers, rather than mucositis or stomatitis. If your examination reveals mouth ulcers rather than a more general inflammation of the mouth, please classify the adverse event as such. Please follow the paradigm below for treatment of stomatitis/oral mucositis/mouth ulcers:

1. For mild toxicity (grade 1), use conservative measures such as **non-alcoholic mouth wash or salt water (0.9%) mouth wash** several times a day until resolution.

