Additional chest x-rays or CT scans may be performed when clinically necessary. If non-infectious pneumonitis develops, a consultation with a pulmonologist should be considered. If the patient develops grade 3 pneumonitis, treatment with RAD001 should be interrupted and the patient should be treated as medically indicated (short course corticosteroids, oxygen, etc). Management of non-infectious pneumonitis suspected to be associated with RAD001 and dose modifications instructions are provided in Table 6.3.

Table 6-3 Management of non-infectious pneumonitis

Worst Grade Pneumonitis	Required Investigations	Management of Pneumonitis	RAD001 Dose Adjustment
Grade 1	CT scans with lung windows and required pulmonary function testing includes: spirometry, DLCO, and room air O ₂ saturation at rest. Repeat a chest x-ray/CT scan every 2 cycles until return to baseline.	No specific therapy is required.	Administer 100% of RAD001 dose.
Grade 2	CT scan with lung windows and pulmonary function testing includes: spirometry, DLCO, and room air O ₂ saturation at rest. Repeat each subsequent cycle until return to baseline. Consider a bronchoscopy.	Symptomatic only. Prescribe corticosteroids if cough is troublesome.	Reduce RAD001 dose until recovery to < grade 1. RAD001 may also be interrupted if symptoms are troublesome. Patients will be withdrawn from the study if they fail to recover to < grade 1 within 3 weeks.

Grade 3	CT scan with lung windows and pulmonary function testing includes: spirometry, DLCO, and room air O ₂ saturation at rest. Repeat each subsequent cycle until return to baseline. Bronchoscopy is required	Prescribe corticosteroids if infective origin is ruled out. Taper as medically indicated.	Hold treatment until recovery to < grade 1. May restart protocol treatment within 2 weeks at a reduced dose (by one level) if evidence of clinical benefit.
Grade 4	CT scan with lung windows and required pulmonary function testing includes: spirometry, DLCO, and room air O ₂ saturation at rest. Repeat each subsequent cycle until return to baseline. Bronchoscopy is required.	Prescribe corticosteroids if infective origin is ruled out. Taper as medically indicated.	Discontinue treatment.

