
For patients with baseline results: Positive HBV-DNA OR positive HBsAg ----- ----- reactivation is defined as: [Increase of 1 log in HBV-DNA relative to baseline HBV-DNA value OR new appearance of measurable HBV-DNA] AND ALT elevation x 5 ULN
	
Treat: Start a second antiviral AND Interrupt study drug administration until resolution:
 
 • ≤ grade 1 ALT (or baseline ALT, if > grade 1) and • ≤ baseline HBV-DNA levels 
If resolution occurs within ≤ 28 days study drug should be re-started at one dose lower, if available. (see Table 1 – Study drug dose reductions) If the patient is already receiving the lowest dose of study drug according to the protocol, the patient should restart at the same dose after resolution. Both antiviral therapies should continue at least 4 weeks after last dose of study drug.
 
If resolution occurs > 28 days Patients should discontinue study drug but continue both antiviral therapies at least 4 weeks after last dose of study drug.

For patients with baseline results: Negative HBV-DNA and HBsAg AND [Positive HBs Ab (with no prior history of vaccination against HBV), OR positive HBc
	
Treat : Start first antiviral medication AND Interrupt study drug administration until resolution:
 
 • ≤ baseline HBV-DNA levels 
If resolution occurs within ≤ 28 days study drug should be re-started at one dose lower, if available. (see Table 1 – Study drug dose reductions) If the patient is already receiving the lowest dose of study drug according to the protocol, the patient should restart at the same dose after resolution. Antiviral

Abj ----- ----- reactivation is defined as: New appearance of measurable HBV-DNA
	
therapy should continue at least 4 weeks after last dose of study drug. If resolution occurs > 28 days Patients should discontinue study drug but continue antiviral therapy at least 4 weeks after last dose of study drug.

--	--

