* All reactivations of hepatitis B are to be recorded as grade 3 (CTCAE v 3.0 Metabolic Laboratory/Other: Viral Re-activation), unless considered life threatening by the investigator; in which case they should be recorded as grade 4 (CTCAE v 3.0 Metabolic Laboratory/Other: Viral Re-activation). Date of viral reactivation is the date on which both DNA and ALT criteria were met (e.g. for a patient who was HBV-DNA positive on 01-JAN-10 and whose ALT reached $\geq 5 \times \text{ULN}$ on 01-APR-10, the date of viral reactivation is 01-APR-10).

Monitoring for hepatitis C

The following two categories of patients should be monitored every 4–8 weeks for HCV reactivation:

- Patients with detectable HCV RNA-PCR test at baseline.
- Patients known to have a history of HCV infection, despite a negative viral load test at baseline (including those that were treated and are considered ‘cured’)

For definition of hepatitis C reactivation and the management guidelines, see Table 6 Guidelines for management of hepatitis C.

Table 6-6 Guidelines for management of hepatitis C

HCV reactivation*	

For patients with baseline results: Detectable HCV-RNA, reactivation is defined as: ALT elevation x 5 ULN
	Discontinue study drug

For patients with baseline results: Knowledge of past hepatitis C infection with no detectable HCV-RNA, reactivation is defined as: New appearance of detectable HCV-RNA
	Discontinue study drug

- All reactivations of hepatitis C are to be recorded as grade 3 (CTCAE v 3.0 Metabolic Laboratory/Other: Viral Re-activation), unless considered life threatening by the investigator; in which case they should be recorded as grade 4 (CTCAE v 3.0 Metabolic Laboratory/Other: Viral Re-activation).

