6.3.4 Follow-up for toxicities while receiving RAD001

Patients who interrupt or permanently discontinue RAD001 due to an adverse event or abnormal laboratory value must be followed at least weekly via telephone for 28 days after the last dose of RAD001, and subsequently at monthly intervals until resolution or stabilization of the event, whichever comes first. If a patient requires a RAD001 dose delay of > 21 days from the intended day of the next scheduled dose, then the patient should be discontinued from the study.

All patients will be followed for adverse events and serious adverse events for 28 days following the last dose of RAD001.

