****This list of clinically relevant drug interactions is updated as of December 02, 2009****

6.3.6 Study drug discontinuation

Study drug must be discontinued for a given patient if the investigator determines that continuing it would result in a significant safety risk for that patient. Patients who, in the opinion of the investigator, require alternative medical therapy, will be discontinued from the study. Patients with a progression will be discontinued from the study. Patients who become pregnant during the study must be withdrawn. If the treatment has to be interrupted for more than 21 consecutive days for any reason, the patient will be discontinued from the study unless otherwise discussed with the study coordinator. In case of patient's discontinuation, the end of study evaluation will be completed as soon as possible. End of study evaluations will include adverse events, concomitant medications and therapies, physical examination, vital signs, ECOG performance status, biochemistry, hematology and tumor measurement.

Patients who discontinue prematurely due to significant AE should continue to be followed-up until resolution of the AE, and the relevant sections of the CRF should be completed as appropriate. Patients who are discontinued due to clinically significant abnormalities in clinical laboratory results should continue to be evaluated until the abnormality resolves or is judged to be permanent.

It will be documented whether or not each patient completed the clinical study. If, for any patient, the study treatment was discontinued the reason will be recorded. Reasons that a patient may discontinue participation in a clinical study are considered to constitute one of the following:

1. Adverse event(s)
2. Abnormal laboratory value(s)
3. Abnormal test procedure result(s)
4. Unsatisfactory therapeutic effect
5. Subject's condition no longer requires study treatment

6. Protocol violation which affect the safety of the patient
7. Subject withdraws consent
8. Lost to follow-up
9. Administrative problems
10. Death

Progressive disease is defined as unsatisfactory therapeutic effect.

For patients who are lost to follow-up, the investigator should show “due diligence” by documenting in the source documents steps taken to contact the patient, e.g. dates of telephone calls, registered letters, etc.

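### Hepatitis B reactivation resolving on days 22 to 28 is both a restart and a discontinuation under the protocol's interruption rules; grade 3 pneumonitis has a lesser conflict over the recovery grade

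*Protocol*

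**What the plan says.** **Hepatitis B.** Protocol Table 6-5 interrupts study drug at reactivation. For both baseline groups it restarts the drug, one dose level lower where one is available, "If resolution occurs within ≤ 28 days". Discontinuation is reserved for the other branch, "If resolution occurs > 28 days".

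**General limits.** Four places set a limit that is not specific to one toxicity:

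- Table 6-2, last row: "Any hematological or non-hematological toxicity requiring interruption for" three weeks or more leads to discontinuation of RAD001.
- Section 6.3.3, on monitoring suspected toxicities: after a dose delay of more than 21 days the patient must leave the study.
- Section 6.3.4: "If a patient requires a RAD001 dose delay of > 21 days from the intended day of the next scheduled dose", the patient should be discontinued.
- Section 6.3.6: "If the treatment has to be interrupted for more than 21 consecutive days for any reason, the patient will be discontinued from the study". The sentence goes on to allow an exception after discussion with the study coordinator.

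**Grade 3 pneumonitis.** The grade 3 non-hematological row of Table 6-2 interrupts until grade 1 or lower and then reintroduces at the lower dose level. It excepts only hyperlipidemia, and it names pneumonitis: "For pneumonitis, consider the use of a short course of corticosteroids (see table 6.3"). Table 6-3 instead says "Hold treatment until recovery to < grade 1", and allows a restart within two weeks at one level lower if there is evidence of clinical benefit.

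**The concern.** A site following Table 6-5 and a site following any of the four general limits would do opposite things with the same patient. These are safety instructions, and the protocol has no sentence ranking them. Section 5.2 lists study drug discontinuation among the reasons for mandatory withdrawal, so stopping the drug and leaving the study amount to the same thing here. What is at stake is uniform management across centers and how long a patient remains on drug.

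For pneumonitis the stake is narrower: whether a grade 3 case that has improved to grade 1 resumes treatment then or waits.

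**Working it through.** No sample size, power or error rate is involved. The check sets the rules side by side and counts the days on which they disagree.

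**Counting assumption.** Let day *n* be the number of consecutive days off drug when reactivation resolves, counted from the first missed dose. Table 6-5 does not say where its 28 days begin. Sections 6.3.3 and 6.3.4 count from the intended day of the next dose, which under daily dosing is the first missed dose. If the 28 days ran from an earlier date, such as the date of reactivation, the overlap would be shorter.

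| Resolution on day | Table 6-5 | Table 6-2 (3 × 7 = 21 days or more) | 6.3.3 and 6.3.4 (more than 21) | 6.3.6 (more than 21) |
|---|---|---|---|---|
| up to 20 | restart | limit not reached | limit not reached | limit not reached |
| 21 | restart | discontinue | limit not reached | limit not reached |
| 22 to 28 | restart | discontinue | discontinue | discontinue, unless discussed with coordinator |
| 29 or later | discontinue | discontinue | discontinue | discontinue, unless discussed with coordinator |

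- Table 6-5 against all four general limits: 28 − 22 + 1 = 7 days.
- Table 6-5 against Table 6-2: 28 − 21 + 1 = 8 days.
- The general limits against each other: they differ on day 21, and only 6.3.6 provides an exception. Section 6.3.3 uses mandatory wording where 6.3.4 uses advisory wording.

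**Do the general limits reach hepatitis B?** None of them excludes it. The footnote to Table 6-5 gives reactivation a toxicity grade: "All reactivations of hepatitis B are to be recorded as grade 3", or grade 4 if life-threatening. Section 6.3.6 applies whatever the cause of the interruption.

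**Is the window realistic?** In both groups, resolution requires HBV-DNA to be back at or below baseline. The HBV-DNA monitoring intervals in Table 6-4 are about every 4 to 8 weeks, or about every 4 weeks, depending on baseline status. Four weeks is 4 × 7 = 28 days. If no extra tests were done after reactivation, confirmation could easily come after day 21. The documents do not say whether extra tests would be done.

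**Pneumonitis.** At grade 2 there is no conflict between the tables, because Table 6-2 excludes pneumonitis there and refers to Table 6-3. At grade 3 there is no such exclusion. A patient who has improved to exactly grade 1 satisfies Table 6-2 and not Table 6-3: one reading restarts, the other continues the hold.

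**The case against.** **The specific rule overrides the general one.** A sensible investigator might take Table 6-5 as the rule for hepatitis B. The protocol does not say so, and where its authors wanted an exclusion they wrote one, as in the grade 2 row of Table 6-2. The wording of 6.3.3 is mandatory and carries no exception.

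**Section 6.3.6 allows an exception.** It does, and that could reconcile individual cases. But a discussion case by case is not the same as a standing instruction to restart, and the other three places have no such clause.

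**Table 6-2 and the monitoring paragraph of 6.3.3 concern suspected RAD001 toxicity.** If a reactivation were judged unrelated to the drug, those two might not apply. Section 6.3.6 still would.

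**Pneumonitis is assigned to Table 6-3.** This has force. Section 6.3.3 says that dose modification for pneumonitis suspected to be due to RAD001 is found in Table 6-3. The grade 3 row of Table 6-2 points to that table too, although the pointer follows the corticosteroid advice. Table 6-3 is thus the more natural authority, and the fault is that Table 6-2 still covers pneumonitis with a different recovery grade. The conflict also depends on one sign. Tables 6-2 and 6-5 use at-or-below, and a lost underline in the available text could explain the difference. The strict sign appears three times in Table 6-3, but the original should be checked.

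**Stronger pneumonitis readings.** A reader might infer that grade 3 pneumonitis patients are either kept or withdrawn. At grade 1 the immediate difference is only restart or continued hold; discontinuation follows only if a time limit then passes. Nor does the two-week restart window in Table 6-3 contradict the three-week limit, since a narrower window for one toxicity can sit under a general ceiling.

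**Few patients are affected.** This is fair. Acute or chronic liver disease is among the exclusion examples, the documents give no expected frequency, and Amendment 7 reports enrollment complete with two patients on drug on 23 July 2013.

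**Conclusion.** The hepatitis B conflict stands in the current protocol text. It covers seven days (22 to 28) against all four general limits, and eight against Table 6-2, on the counting assumption stated above. The disagreement among the general limits also stands. The pneumonitis conflict stands as a secondary point, for grade 3 only and subject to checking the sign in Table 6-3.

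The consequence is inconsistent safety management and time on drug. A reader might go further and infer that the contradiction distorts the primary result through progression or unknown classifications, a changed analysis set, or replacement of withdrawn patients. The documents do not support that:

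- SAP section 1.4.1 counts discontinuation without radiologic progression as progression when the reason is unsatisfactory effect, new cancer therapy or death. Adverse events and abnormal laboratory values are separate reasons in Protocol 6.3.6 and are not on that list.
- One stable-disease assessment more than six weeks after start avoids the unknown category. Only a patient stopped without one remains exposed to it.
- The SAP's primary analysis uses the ITT set, which keeps any patient who was dosed and had one post-baseline tumor assessment.
- Replacement under section 5.2 no longer matters once enrollment is complete.

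The effect on the primary result is therefore probably small. It cannot be quantified, because no event frequency is given.

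**What to change.** Amend the protocol wording in two places.

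1. Reconcile Table 6-5 with the last row of Table 6-2 and with sections 6.3.3, 6.3.4 and 6.3.6. State which rule governs hepatitis B reactivation, where the day count starts, whether exactly 21 days is inside or outside the general limit, and whether an exception is allowed. If one is, put it in every place that states the limit.
2. Reconcile the grade 3 row of Table 6-2 with Table 6-3, so that one recovery grade applies to pneumonitis and one table is named as governing.

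The values are for the clinical team; none is proposed here. The cost is amendment text and the ethics approval that goes with it. No design figure or analysis changes. Amendment 7 was already revising section 6, and the rules still applied to the two patients then on drug.

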6.3 Treating the patient

6.3.1 Instructions for prescribing and taking the study drug

RAD001 will be dispensed by the study center personnel on an outpatient basis. Patients will be provided with an adequate supply of RAD001 for self-administration at home.

RAD0001 will be dosed starting on Week 1 Day 1. Patients will be instructed to take two tablets of RAD001 orally with a glass of water, once daily at the same time each day, in a fasting state or after no more than a light, fat-free meal. If vomiting occurs, no attempt should be made to replace the vomited dose. Patients should be requested to bring their unused medication, including the empty blister packs, to the clinic at each visit. Compliance should be verified by the investigator's staff through counting the number of tablets consumed between visits.

The investigator (or his/her designee) will document dosage administration and all dose changes during the study in the CRF. The site must maintain an overall drug accountability log for the study, as well as individual accountability records for each patient. The dose, amount dispensed, amount received, and amount remaining unused must be recorded in the source document. Drug accountability will be noted by the field monitor during site visits and at the completion of the study. The patient will be asked to return all unused RAD001 at the end of study treatment.

Patients will be treated with RAD001 until progression of tumor, the occurrence of unacceptable toxicity, or until the investigator or patient decides that continuation is not in the best interest of the patient. Interruption for toxicity should follow the instructions in Table 6.2.

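### Table 6-5 gives life-threatening (grade 4) hepatitis B reactivations the same restart rule as grade 3, against the grade 4 stop in Table 6-2, and no text ranks the two tables (minor)

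*Protocol*

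**What the plan says.** Protocol section 6.3.3 carries the heading "Management of RAD001 toxicities" and contains both tables.

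- **Table 6-5, hepatitis B.** There are two rows, chosen by baseline serology. In both, drug is interrupted until resolution. If that comes within 28 days, "study drug should be re-started at one dose lower, if available". A patient already at the lowest level is covered too: "the patient should restart at the same dose after resolution". After 28 days the drug is stopped. Neither row is split by grade.
- **Footnote to Table 6-5.** "All reactivations of hepatitis B are to be recorded as grade 3", "unless considered life threatening by the investigator; in which case they should be recorded as grade 4". The footnote sets how the event is graded and dated. It gives no drug action.
- **Table 6-2.** Its title is "Criteria for dose-modification in case of suspected RAD001 toxicity and re-initiation of RAD001 treatment". The grade 4 row of the non-hematological block reads "Discontinue RAD001", with no exception for hepatitis.
- **Routing.** The hepatitis text in section 6.3.3 refers reactivation to the hepatitis B table, and section 4 ties the management guidelines to baseline viral load and serology. Section 6.3.1 says "Interruption for toxicity should follow the instructions in Table 6.2".
- **General stopping rules.** Section 5.2 requires withdrawal for unacceptable toxicity. Section 6.3.1 ends treatment for unacceptable toxicity, or when the investigator or patient judges that continuing is not in the patient's best interest. Section 6.3.6 requires discontinuation when the investigator sees a significant safety risk.

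**The concern.** The footnote shows that the authors foresaw life-threatening reactivations, but the table treats them like any other. A site facing a RAD001-suspected grade 4 reactivation that settles quickly can find two opposite instructions in the same section. Two sites could handle the same event differently, each citing protocol text.

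If Table 6-5 is taken to govern, the conflict goes away but the written default is then to restart the drug after an event that the investigator called life-threatening. In the second row (HBV-DNA and HBsAg negative at baseline) the only condition for restart is HBV-DNA back at or below baseline. The first row also asks for ALT recovery.

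What is at stake is consistent safety management of individual patients. No efficacy analysis depends on it.

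**Working it through.** No stated figure bears on this point, so the check is to follow one case through each rule and then count how section 6.3.3 treats grade 4 elsewhere.

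**Case.** Hepatitis B reactivation, suspected to be related to RAD001, judged life-threatening (so recorded as grade 4), resolved on day 20 of the interruption.

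| Rule | Trigger | At day 20, grade 4 | Instruction |
|---|---|---|---|
| Table 6-5, both rows | resolution within 28 days | 20 ≤ 28, met | restart one level lower, or same dose if at the lowest |
| Table 6-2, non-hematological grade 4 | suspected toxicity, grade 4 | met | discontinue |
| Table 6-2, length of interruption | 3 weeks or more (3 × 7 = 21 days) | 20 < 21, not met | none |
| 6.3.3 (toxicity monitoring), 6.3.4, 6.3.6 | more than 21 days | not met | none |
| Table 6-5, late resolution | more than 28 days | not met | none |

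No duration rule is reached at day 20, so the opposite instructions come from grade alone. The grade 4 clash continues up to day 28. From day 21 the 28-day window also meets the 21-day limits whatever the grade; that is a separate matter, and the 20-day case is chosen to keep it out.

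The event reaches the non-hematological row because the footnote codes it under a metabolic/laboratory term. At grade 3 the tables agree in outline: both interrupt and resume at a lower dose.

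**Other grade 4 rules in section 6.3.3.**

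- Table 6-2, non-hematological: discontinue.
- Table 6-2, thrombocytopenia: discontinue.
- Table 6-2, febrile neutropenia: discontinue.
- Table 6-3, pneumonitis: discontinue.
- Table 6-2, neutropenia: interrupt, then resume at the lower level.

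That is 4 of 5 that stop the drug. In Table 6-5, 0 of 2 rows set grade 4 apart. Febrile neutropenia already has the split that Table 6-5 lacks: the form labelled not life-threatening (grade 3) resumes lower, and the life-threatening form (grade 4) stops. Table 6-6 stops the drug for hepatitis C reactivation in both rows at any grade.

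**Patients who could be affected.** The Amendment 7 rationale states that enrollment was complete in all three arms and that one patient in arm II and one in arm III were on drug at 23 July 2013: 1 + 1 = 2. The documents do not give their hepatitis B status.

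**The case against.** The strongest reply is that Table 6-5 is self-contained and governs.

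- Its header takes in every reactivation, with or without symptoms, and carries the mark that leads to the grading footnote. So the table does state an action for grade 4, namely the same one as for grade 3. A reader might infer that it leaves grade 4 without any instruction; the header does not support that. What is missing is a separate action.
- The hepatitis text points to it directly, whereas the sentence in section 6.3.1 is general.
- Table 6-6 shows that the hepatitis tables can depart from Table 6-2 without a stated exception: it stops the drug for hepatitis C reactivation that is recorded as grade 3 by default, where the grade 3 row of Table 6-2 would interrupt and resume.
- Recovery to grade 1 or better, the restart test in Table 6-2 for grade 3, does not suit an event that can only be recorded as grade 3 or 4. Table 6-5 supplies its own test.

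These points stand and make Table 6-5 the likelier operative table. They do not amount to a precedence rule. For pneumonitis, Table 6-2 names the table to use; for hepatitis it does not. Table 6-3, also specific to one event, keeps the grade 4 stop.

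A second reply is that the risk is already covered. A reader might infer that the protocol compels a restart after a life-threatening event. It does not: sections 5.2, 6.3.1 and 6.3.6 allow or require the investigator to stop, and the same investigator decides whether the event was life-threatening. That limits the harm, but it leaves the outcome to case-by-case judgement against a written default that points the other way.

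A third reply is that stopping at grade 4 is a preference, since grade 4 neutropenia resumes. That is fair. The documents give no evidence that permanent discontinuation is better once a reactivation has resolved under antiviral treatment. The argument for the change is consistency with most of section 6.3.3.

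**Conclusion.** The point holds as a minor inconsistency in safety management, with medium confidence. Table 6-5 does not separate the life-threatening reactivations that its own footnote provides for, and for a RAD001-suspected grade 4 event resolved within 20 days it says restart where Table 6-2 says discontinue.

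The conclusion assumes that the event is suspected to be drug-related (the scope of Table 6-2) and that it counts as non-hematological. It does not depend on which table governs: if neither is ranked, the instructions conflict; if Table 6-5 governs, restart is the default after a life-threatening event. Confidence is medium because the second reading is the likelier one and turns the matter into a questionable choice more than a contradiction.

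The reach is small: from Amendment 7 on, at most two patients, and only if one of them has this particular event. A reader might infer a wider exposure or an effect on the trial's results. Completed enrollment rules out the first, and nothing in the endpoints, error rates or sample sizes depends on these tables.

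**What to change.** Amend both rows of Table 6-5. Limit the interrupt-and-restart instruction to grade 3 reactivations and add a line such as: *Grade 4 (life-threatening), suspected to be related to RAD001: stop study drug permanently as in Table 6-2; keep antiviral treatment going (both agents in the first row) for 4 weeks or longer beyond the final dose.* This follows the split that Table 6-2 already makes for febrile neutropenia. A grade 4 reactivation not suspected to be drug-related falls outside Table 6-2, so the amendment should also say whether it keeps the restart option.

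If the sponsor does intend restart after grade 4, a hepatitis B exception in the grade 4 row of Table 6-2, pointing to Table 6-5, would also remove the contradiction. It would leave restart as the default.

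The cost is one added line in each of two cells, by amendment, with no new visits, procedures or patients. The downside is that a patient who recovers from a life-threatening, RAD001-suspected reactivation loses the option to restart. That could concern at most the two patients on drug at 23 July 2013.
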